5.2 Evaluations during Radiation Therapy

- Weekly history and physical including performance status (Zubrod), and toxicity.

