5.4 Post-treatment Evaluations

- History and physical, performance status (Zubrod), and toxicity at 6 weeks, 3 months, and then every 6 months for 5.25 years after completion of RT.
- Blood (up to 5 tubes) work in relation to RT:
 - PSA at 6 weeks, 3 months, and then every 6 months for 5.25 years.
 - Serum total testosterone 9 months after completion of RT.
 - Blood for research fluid tests will be collected at 3 months, 9 months and 2-2.5 years after completion of RT.
- DCE-MRI and or PET with timed contrast at 3 months, 9 months, and 2-2.5 years after completion of RT.
 - Should a lesion be identified, the treating physician will discuss management decisions with the participant
- Bone scan for a PSA of ≥ 2 or physician concern for metastasis.
- Psychosocial questionnaires will be administered at follow-up at 6 weeks, 3 months, 9 months, 15 months and yearly to 5.25 years:
 - Memorial Anxiety Scale for Prostate Cancer patients (MAX-PC).
 - The Expanded Prostate Cancer Index Composite Questionnaire-SF-12 (EPIC-SF12).

- International Prostate Symptom Scale (IPSS) will be done at each follow-up visit for 5.25 years. This includes 6 weeks, 3 months and every 6 months after RT for 5.25 years.

Note: Measurements and follow-up visits should occur within \pm 2 weeks up to the 3 months visit and within \pm 8 weeks for subsequent measurements/visits

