9.1 Definitions

- *PSA response rate*: The proportion of study patients with PSA <0.1 ng/mL at 21 months after completion of study treatment.
- *Acute toxicity*: Toxicity occurring during treatment and within three months of completing treatment.
- *Late toxicity*: Toxicity occurring more than three months after treatment completion. *Failure rate*: The cumulative incidence of biochemical or clinical failure allowing for competing risk as needed. Clinical failure is defined as at least a 25% increase in the size of the tumor relative to the smallest volume recorded, or new extension of tumor beyond the capsule, or re-extension of tumor beyond the capsule after initial regression, or urinary obstructive symptoms with carcinoma found at TURP. Biochemical failure is defined as PSA \geq nadir + 2 ng/mL.

- *Failure-free Survival (FFS)*: The elapsed time from start of radiotherapy to first documented evidence of biochemical or clinical failure or death from any cause, whichever occurs first. In the absence of any event defining failure, follow-up time will be censored at the date of last documented failure-free status.
- *Overall Survival (OS)*: The elapsed time from start of radiotherapy to death from any cause. For surviving patients, follow-up will be censored at the date of last contact.
- *Biomarker expression*: Quantification of the amount of the biomarker specific immunohistochemical staining in the area of tumor.
- *QOL*: Two contemporary instruments will be utilized to assess patient function and bother (Expanded Prostate Cancer Index Composite-SF12 (EPIC-SF12) and prostate cancer-specific anxiety Memorial Anxiety Scale for Prostate Cancer patients (MAX-PC).

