Time to event endpoints will be analyzed by Kaplan-Meier (KM) or competing risk (CR) methods as indicated in Table 14.5.[53, 54] Where the Kaplan Meier method is used, point estimates and 2-sided 95% confidence intervals for event-free rates will be reported for selected times such as 1, 2 and 5 years from treatment start using Greenwood's variance and the log-log transform method. Median event-free or overall survival time, if attained, will also be reported. Cox regression models will be used to explore the prognostic effect of baseline characteristics as well as biomarkers and proteomic and genomic profiles. Regression findings will be expressed as hazard ratios and corresponding 95% confidence intervals. For analyses involving competing risks, cumulative incidence rates will be reported for selected times with corresponding 2-sided 95% confidence intervals based on the variance estimator of Aalen and the log-log transform method. Regression models investigating prognostic factors will be fit by the method of Fine and Gray. [55, 56] Where study data indicate that at most a small number of competing risk events have occurred, analysis will be simplified by treating such events as censored observations in a Kaplan-Meier analysis, since the resulting overestimation of the event rate will be negligible.

Table 14.5. Time-to-event endpoints.

Endpoint	Analysis	Events (earliest)	Competing risks	Censoring
Failure rate	CR	CF, BF, BF+ CF (within 6 months of each other). Start subsequent therapy. Death related to prca without prior evidence of failure.	Death unrelated to prca	Last clinical +PSA assessment
Toxicity rate (to be done separately for GI and GU)	CR	Onset of grade 2+ and 3+ toxicity	Start subsequent therapy Death, any cause	Last contact
Failure free survival (FFS)	KM	CF, BF, BF+ CF. Start subsequent therapy. Death, any cause.	n/a	Last clinical or PSA assessment
Prostate cancer mortality	CR	Death related to prca	Death unrelated to prca	Last contact
Overall survival (OS)	KM	Death, any cause	n/a	Last contact

KM: Kaplan-Meier. **CR:** competing risk. **BF:** Biochemical failure. **CF:** clinical failure. **prca:** prostate cancer. **GI:** gastrointestinal. **GU:** genitourinary.

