APPENDIX I. STUDY CALENDAR – MAPS

Assessment	Prior to Enrollment	After Enrollment and Prior to RT	Weekly during RT	Follow-up				
				During Last Week of RT	6 Weeks after RT	3 Months after RT	Every 6 months thereafter up to 5.25 years post-RT	Other
History & Physical Exam; Performance Status (Zubrod) Within 8 weeks prior to protocol entry and Zubrod < 2.	X		X	X	X	X	X	
Toxicity During RT and at all follow-up visits; use CTCAE 4.0.								
PSA PSA of at least 0.1 and up to 4.0 ng/mL and obtained ≤ 3 months prior to enrollment	X ^a			X	X	X	X	
Serum total testosterone Obtained ≤ 3 months prior to enrollment	X ^a							At 9 months
Blood collection for research	X ^a			X		X		At 9 months, 2-2.5 years
Bone Scan	X ^b							©If deemed necessary by treating physician
DCE-MRI and or PET of prostate bed/pelvis Obtained ≤ 3 months prior to enrollment and the enhancing lesion in the prostate bed should be at least 0.4 cc and a maximum of 6 cc	X					X		©At 9 months and 2-2.5 years
Pathology Review of outside biopsy material prior to enrollment	X							
MRI/US prostate bed biopsy If the MRI shows a new lesion, an optional MRI/US-guided biopsy may be obtained						X ^e		©At 9 months and 2 – 2.5 years post completion in case of identified by MRI lesion

EPIC- SF-12, MAX-PC After enrollment and prior to US biopsy.	X			X	X	X		At 9 months, 15 months and yearly to 5.25 years
IPSS	X			X	X	X	X	
CT simulation		X						
Note: Measurements and follow-up visits should occur within \pm 2 weeks up to the 3 month visit and within \pm 8 weeks for subsequent measurements/visits.								
See Eligibility Criteria for detailed description for evaluations.								
^a If possible, blood collected prior to enrollment should be obtained prior to androgen deprivation therapy.								
^b If deemed necessary, obtained \leq 4 months prior to enrollment								
^c To be conducted for a PSA of ≥ 2 or physician concern for metastasis.								
^d MRI at 9 months and 2-2.5 years will be obtained per the PI's discretion.								
^e Biopsy collection is optional								

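### Table 14.5 censors the GI/GU toxicity curves at last contact, not at the last toxicity grading, so late toxicity is modestly understated if any man stays in contact after his toxicity visits stop

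*Combined protocol and SAP*

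**What the plan says.** Section 14.5 plans cumulative incidence curves, from start of treatment, for grade 2+ and grade 3+ toxicity, with GU and GI separate. Table 14.5 gives the toxicity row as "Onset of grade 2+ and 3+ toxicity Start subsequent therapy Death, any cause Last contact": the event, then the two competing risks, then the censoring date.

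Section 9.1 uses that same date for overall survival: "For surviving patients, follow-up will be censored at the date of last contact". The prostate cancer mortality row of Table 14.5 uses it too.

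The other two rows that depend on an assessment are treated differently. Failure rate is censored at "Last clinical +PSA assessment" and failure-free survival at "Last clinical or PSA assessment".

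Toxicity grading is tied to visits. During radiotherapy, section 5.2 has "Weekly history and physical including performance status (Zubrod), and toxicity". Afterwards, section 5.4 has "toxicity at 6 weeks, 3 months, and then every 6 months for 5.25 years after completion of RT". The toxicity row of the Appendix I calendar reads "During RT and at all follow-up visits; use CTCAE 4.0". Section 15.4 lists visit progress notes as the record of treatment toxicity. No section provides for toxicity grading by telephone or chart contact.

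**The concern.** A censoring date should be the last time at which the event could have been seen. For death, that is the last date the man was known to be alive. For graded toxicity, it is the last date on which someone graded it. Where the second date is earlier than the first, the plan counts the interval between them as time at risk without toxicity. A man last graded at 2 years and known alive at 5 years, for example, adds three years to the denominator with little chance of adding an event.

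With complete recording of events before the visits stop, the error runs one way, towards a lower toxicity rate. On-treatment toxicity is graded weekly and is hardly exposed; late toxicity is. Toxicity of the boost is named first among the secondary objectives in section 2.2, and section 14.1 says the trial is meant to inform the design of a later one, so a rule that can only flatter late safety should be corrected.

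**Working it through.** The plan states no toxicity incidence, so there is no figure to reproduce. The check has two parts.

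**1. Do the passages allow contact without grading?**
- Section 14.5 plans five years of follow-up for progression and vital status, and that sentence does not name toxicity.
- The failure-free survival row accepts a PSA result without a clinical assessment as a follow-up date. A PSA alone carries no toxicity grade.
- Last contact is nowhere defined as a contact at which toxicity is graded.

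So the gap is possible. How often it would occur is not stated.

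**2. How large is the effect?** All inputs here are assumptions: exponential toxicity onset with rate λ, and exponential loss of toxicity visits with rate μ, unrelated to toxicity, among men who remain in contact to 5 years. With last-contact censoring and no competing events, the expected 5-year estimate is

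λ/(λ+μ) × [1 − (1 − F)(1 − L)],

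where F is the true 5-year rate, L the share who have stopped visits by 5 years, λ = −ln(1−F)/5 and μ = −ln(1−L)/5.

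- F = 30%, L = 10%: λ = 0.0713, μ = 0.0211. Estimate = 0.772 × (1 − 0.70 × 0.90) = 0.772 × 0.37 = 28.6%.
- F = 10%, L = 10%: λ = μ = 0.0211. Estimate = 0.5 × (1 − 0.90 × 0.90) = 9.5%.

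Both are about 5% low in relative terms.

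A simulation of 400,000 men per scenario added about 5% deaths by 5 years as a competing risk, used the Aalen-Johansen estimator, and varied when visits stop. Results for 10% stopping visits while in contact (5-year incidence, %):

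| When visits stop | Fully observed | Last contact | Last grading | Relative error, last contact |
|---|---|---|---|---|
| Uniform, 0.25-5.25 years | 14.60 | 13.97 | 14.60 | −4.3% |
| Uniform, 0.25-2 years | 14.58 | 13.47 | 14.58 | −7.6% |
| All at 3 months | 14.68 | 13.29 | 14.67 | −9.4% |

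The relative errors were nearly the same at fully observed rates near 10% and 29%. Over shares of 5% to 30% stopping, the understatement ran from about 2% to 29%. Censoring at the last grading recovered the fully observed value, within simulation error, in every scenario.

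**Early onset.** If half of a true 30% occurs before any visits are lost, only the other 15 points are exposed. Applying the same relative loss (28.6/30) gives roughly 15 + 15 × 0.953 = 29.3%.

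**Scale against sampling error.** With 40 men the binomial standard error is √(0.30 × 0.70/40) = 7.2 points at 30%, and √(0.10 × 0.90/40) = 4.7 points at 10%.

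**The case against.** The strongest reply is that the gap is assumed. Toxicity, PSA and IPSS are scheduled at the same follow-up visits to 5.25 years, and no separate survival call is scheduled. For a man simply lost to follow-up, last contact may well be his last clinic visit, and then there is no bias. This stands, and it is why the size can be given only as a range under assumptions.

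Three further points also stand:
- Adverse event reporting in section 11 is not confined to visits, and serious events are followed until resolution or loss to follow-up. Some grade 3+ events would reach the record between visits, so grade 2 is the more exposed.
- The curve is descriptive, with no test or threshold attached, and section 14.5 also tabulates toxicity by type and grade.
- The plausible bias is well inside the sampling error for 40 men.

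The comparison with the failure rows is also imperfect, since a PSA-only date can extend follow-up for clinical failure in failure-free survival. Both rows are nevertheless censored at an assessment of some component of the outcome, and the toxicity row is not.

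None of this makes last contact the better date. If every contact includes grading, the two dates coincide and the correction changes nothing.

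**Conclusion.** The censoring date in the toxicity row is the wrong one for an outcome graded at visits, and any error it causes understates late toxicity. If 10% of men stop toxicity visits by 5 years while in contact, the relative understatement is about 4-9%. It is less if most events are early, and nil if no man is in contact without being graded. The 10% is an assumption. Severity is minor: a correction to a descriptive secondary safety estimate.

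A reader might infer two stronger things.
- One is to take the 10% drop-out in section 14.2 as reached by 21 or by nine months and carry it forward to 5 years. That gives 1 − 0.9^(60/21) = 26% or 1 − 0.9^(60/9) = 50% without visits, and turns a true 30% into 26.1% or 22.1%. The documents do not support this. The 10% is an allowance for evaluability of PSA response; it does not describe men who are still in contact but ungraded, and nothing says it compounds.
- The other is that safety monitoring is compromised. It is not: the stopping guidelines in section 14.6 count events among patients evaluated, or followed long enough for late toxicity, and do not use this cell.

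**What to change.** In the toxicity row of Table 14.5, replace the censoring entry with *date of last CTCAE toxicity assessment*. Keep last contact for overall survival and prostate cancer mortality. Beside each reported cumulative incidence, give the number of men still under toxicity assessment at that time.

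The cost is one table cell and one added line of output, with no new visits or data and no change to the sample size. Late confidence intervals will be slightly wider because fewer men count as at risk.

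The change does not remove all bias if stopping visits is related to toxicity: the curve would still be too low if men with toxicity stop attending, and too high if symptom-free men skip visits. The reported numbers under assessment let a reader judge how much that could matter.

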14.6 Interim monitoring

The Research Team will continuously monitor study accruals, toxicities and clinical outcome. The Sylvester Comprehensive Cancer Center's Data and Safety Monitoring Committee (DSMC) will monitor this protocol according to the Cancer Center's DSM Plan. DSMC oversight of the conduct of this trial includes ongoing review of adverse event data and periodic review of trial outcomes. Additionally, the Sylvester Protocol Review Committee will monitor study progress with respect to patient accrual.

Early stopping for excess toxicity. We propose the following guidelines for the Sylvester DSMC (see also Appendix III) in its review of accumulating data on toxicity of study treatment. The proposed guidelines were developed using Bayesian methods, which can be applied at any stage of enrollment without advance specification of the number of interim analyses to be performed, or the number of patients evaluable for toxicity at the time such assessments are made.[57, 58]

Under the Bayesian method, we assign a prior probability (level of belief at the start of the trial) to a range of possible values for the true toxicity rate. As data on treated patients become available, the prior probability distribution is revised and the resulting posterior probability becomes the basis for recommending either early termination or continuation of the study. Specific stopping guidelines based on posterior probabilities for both acute and late occurring toxicity are given below along with underlying assumptions for the prior distributions.

Acute safety monitoring will be based on the occurrence of treatment related grade 3 or higher GI or GU toxicity occurring during study treatment or within 3 months of treatment completion. Early stopping (suspension and possibly termination) will be considered if there is evidence that the proportion of patients experiencing such toxicity exceeds 15%. Specifically, we suggest as a guideline for early termination a posterior probability of 80% or higher that the rate of grade 3 or higher GI/GU toxicity exceeds 15%. Similarly, we will monitor the rate of grade 3 or higher late occurring toxicity (onset of toxicity 3 months or more after completing RT) and apply a guideline for early termination based on 80% or higher posterior probability that this rate exceeds 10%. The rate of acute and late toxicity will be monitored. **Table 14.6.1** below shows specific instances where these stopping guidelines are met, thus suggesting early termination of the study due to evidence of excessive toxicity.

Table 14.6.1. Stopping rules for toxicity

Number of patients with acute G3+ toxicity*	Total pts evaluated	Observed rate	Number of patients with late G3+toxicity [#]	Total pts evaluated	Observed rate
2	3 to 6	≥33%	2	3 to 8	≥25%
3	7 to 11	≥27%	3	9 to 16	≥19%
4	12 to 16	≥25%	4	17 to 24	≥17%
5	17 to 21	≥24%	5	25 to 32	≥16%
6	22 to 27	≥22%	6	33 to 40	≥15%
7	28 to 33	≥21%	-	-	-
8	34 to 38	≥21%	-	-	-
9	39 to 40	≥23%	-	-	-

* Acute G3+: treatment-related (possible, probable, or definite) grade 3 or higher GI/GU toxicity occurring within 3 months (acute) of RT completion.

Late G3+: treatment-related (possible, probable, or definite) grade 3 or higher GI/GU toxicity occurring more than 3 months (late) after RT completion.

To illustrate the stopping guidelines, suppose that 4 patients have been assessed for toxicity and 3 of them have experienced grade 3 treatment-related toxicity during or within 3 months of completing radiotherapy (second row, left panel). Under this circumstance, the observed rate of acute G3+ toxicity is 37.5%, resulting in a posterior probability of 90.4% that the true underlying rate exceeds 15% thus suggesting early termination of the study due to acute toxicity. Similarly for late G3+, suppose that a total of 8 patients have been followed sufficiently for assessment of late toxicity and 2 have experienced grade 3 treatment-related toxicity starting more than 3 months after treatment completion (first row, right panel). These data give a 25% observed rate of late G3+ toxicity and a posterior probability of 82.6% that the true underlying rate exceeds 10% thus suggesting early termination of the study due to late toxicity.

Posterior probabilities used to derive guidelines for acute toxicity are calculated under a prior beta distribution with parameters $\beta_1 = 0.3$ and $\beta_2 = 1.7$, which corresponds to an expected rate of 15% based

on prior information roughly equivalent to having studied 2 patients. Furthermore, this prior distribution assigns a small a priori chance (32%) to the possibility that the true rate of unacceptable toxicity is 15% or greater. For late toxicity, the parameters of the prior distribution are $\beta_1 = 0.2$ and $\beta_2 = 1.8$, giving an a priori chance of 27% that the true rate of late toxicity is 10% or greater.

No early stopping for efficacy. We do not propose early stopping of this trial based on interim assessment of efficacy for the following reasons. First, it would not be practical or desirable to suspend accrual to accommodate an interim assessment of the primary efficacy endpoint, PSA response, which requires nine months follow-up. Moreover, PSA response is not a perfect near term surrogate for long term benefit and thus not a definitive basis for an early conclusion regarding efficacy. The trial involves standard therapy with dose escalation, and an evaluation of PSA response based on accrual of 24 evaluable patients will provide information needed to design a subsequent trial evaluating long term outcome.

14.7 Reporting and Exclusions

N/A

15.0 INVESTIGATOR'S RESPONSIBILITIES

15.1 Investigator Responsibility/Performance

The investigator will ensure that this study is conducted in accordance with all regulations governing the protection of human subjects and Good Clinical Practices (GCP) guidelines.

The investigator will ensure that all work and services described in or associated with this protocol will be conducted in accordance with the investigational plan, applicable regulations, and the highest standards of medical and clinical research practice.

15.2 Confidentiality

The investigator must ensure that each subject's anonymity will be maintained and each subject's identity will be protected from unauthorized parties. A number will be assigned to each subject upon study entry and the number and the subject's initials will be used to identify the subject for the duration of the study. The investigator will maintain all documents related to this study in strict confidence.

15.3 Informed Consent and Permission to Use Protected Health Information

It is the responsibility of the investigator to obtain written informed consent from each subject participating in this study after adequate explanation, in lay language, of the methods, objectives, anticipated benefits, and potential hazards of the study. The investigator must also explain that the subject is completely free to refuse to enter the study or to discontinue participation at any time (for any reason) and receive alternative conventional therapy as indicated. Prior to study participation, each subject will sign an IRB approved informed consent form and receive a copy of same (and information leaflet, if appropriate). For subjects not qualified or able to give legal consent, consent must be obtained from a parent, legal guardian, or custodian.

The investigator or designee **must** explain to the subject before enrollment into the study that for evaluation of study results, the subject's protected health information obtained during the study may be shared with the study sponsor, regulatory agencies, and the IRB. It is the investigator's (or designee's) responsibility to obtain permission to use protected health information per HIPAA from each subject, or if appropriate, the subjects' parent or legal guardian.

15.4 Source Documentation and Investigator Files

The investigator will maintain adequate and accurate records to fully document the conduct of the study and to ensure that study data can be subsequently verified. These documents will be classified into two separate categories: 1) investigator study file and (2) subject clinical source documents that corroborate data collected on the CRF's. Subject clinical source documents will include hospital/clinic patient records; physician's and nurse's notes; original laboratory, radiology, pathology, and quality of life surveys, signed informed consent forms. When the CRF or any form is used as the source document, this will be clearly stated in the investigator study file.

At a minimum, the following documents will be collected:

- Medical history/physical condition and diagnosis of the subject before involvement in the study sufficient to verify protocol entry criteria
- Study number, assigned subject number, and verification that written informed consent was obtained (each recorded in dated and signed notes on the day of entry into the study)
- Progress notes for each subject visit, including treatment toxicity
- Documentation of treatment
- Laboratory test results
- Adverse events (action taken and resolution)
- Condition and response of subject upon completion of or early termination from the study
- Quality of life surveys
- DCE-MRI tumor size and location generated by the in-house developed software
- Radiation treatment Dose Volume Histograms.

